Subjects will receive \$250 for completion of the inpatient visit. There is no compensation for the screening visit. If a subject is asked to repeat a study due to technical problems, he/she will receive an additional \$250.

Monitoring Entity:

This investigation will be monitored by [name] [name]. [name] has no commercial interest in any of the companies which manufacture any of the devices used in this study.

Data Collection:

Subject privacy will be protected by using a three-digit identifying number to code study documents. Study staff will record data required by the protocol onto the paper Case Report Forms (CRF). Only a subject demographics/enrollment log case report form will be entered into REDCAP, a clinical research electronic data application designed to support traditional case report form data capture for research studies housed at Oregon Health Science University and administered by the Oregon Clinical and Translation Research Institute (OCTRI). Investigators and research coordinator will verify that the procedures are conducted according to the approved protocol. All paper source documents will be kept in a locked cabinet for a minimum of five

years. All data from the study files on the Android Nexus 5 phone will subsequently be entered into the authorized electronic REDCAP Cloud database.

Data Repository

The de-identified data collected during this study will be used for analysis of the primary and secondary endpoints listed in this protocol. This data will also be stored in the OregonAPC repository according to IRB protocol 19858. The purpose of this data repository is to store the following de-identified data collected during the study described in this protocol: 1) blood glucose data, 2) sensor and blood glucose data, 3) insulin infusion data 4) blood ketone data, 5) rescue carbohydrate data, 6) meal data and 7) responses to questionnaires. There are no biological specimens collected from this study that will be stored in the repository.

Recording of Data:

Investigators and staff will record data collected during the clinical trial on the CRF's. Case report forms (CRF) for this study will be paper forms only. The CRFs will include:

1. Screening form
2. Day 1 Inpatient Closed-loop Study Visit
3. Phone Update Form
4. Adverse Event form
5. Serious Adverse Event form
6. Concomitant Medications

The Principal Investigators may authorize other personnel to make entries in the CRF.

Monitoring Procedures:

This protocol is written in accordance with the principles established by the 18th World Medical Assembly General Assembly (Helsinki, 1964) and amendments and clarifications adopted by the 29th (Tokyo, 1975), 35th (Venice, 1983), 41st (Hong Kong, 1989), 48th (Somerset West, South Africa, 1996), 52nd (Edinburgh, 2000), 53rd (Washington, 2002), 55th (Tokyo, 2004), 59th (Seoul, 2008), and 64th (Brazil, 2013) General Assemblies. The investigator will ensure that the study described in this protocol is conducted in full conformance with those principles, the protocol, current FDA regulations, ICH Good Clinical Practices (GCP) guidelines, Good Laboratory Practices (GLP) guidelines, local ethical and regulatory requirements, including the Federal Food, Drug and Cosmetic Act, U.S. applicable Code of Federal Regulations (title 21), any IEC requirements relative to clinical studies.

Should a conflict arise, the investigator will follow whichever law or guideline affords the greater protection to the individual subject. The investigator will also ensure thorough familiarity with the appropriate use and potential risks of use of the study device, as described in this protocol, prior to the initiation of the study.

Unanticipated problems will be detected by reviewing descriptions of known or foreseeable adverse events and risks in the IRB-approved research protocol and the current IRB approved consent form, any underlying disease or conditions of the subject experiencing the adverse event,

a careful assessment of whether the adverse event is related or possibly related to the subject's participation in the study.

Triggers for reporting unanticipated problems are seizure, hospitalization, death or any other occurrence considered serious by the PI. If ongoing monitoring of the closed-loop studies reveals studies repeatedly being terminated because of unresponsive hyperglycemia or repeated serious hypoglycemia (resulting in altered mental status, loss of consciousness, or seizure) believed not amenable to revisions in control system parameter tuning, then the study will be discontinued immediately. If studies in two subjects are stopped for severe hypoglycemia or severe hyperglycemia, then the entire study will be halted. Severe hypoglycemia is defined as an event requiring the assistance of another person to administer carbohydrate, glucagon or resuscitative actions. Severe hyperglycemia is defined as 1) venous blood glucose exceeds 400 mg/dl on two occasions (120 min or more apart within a 4 hour window), 2) venous blood glucose exceeds 400 mg/dl on two occasions more than 120 minutes apart but outside of the 4 hour window and during that time, the venous blood glucose has not fallen below 250 mg/dl, or 3) serum ketones are above 1.5 mM at any time. In addition, if there is any unexpected event such as death or patient hospitalization, the studies will be stopped until the root cause is evaluated.

Any adverse event (AE) and/or unanticipated problem (UP) will be reported to the investigator monitor immediately by one of the investigators. Hypo- and hyperglycemia will not be considered AEs unless subject has positive ketones or displays symptoms of hypoglycemia such as: loss of consciousness, slurred speech, hospitalization or EMS services called. One of the investigators will always be on-call during the closed-loop studies and will write up a description of the adverse event/unanticipated problem. All reportable new information (RNI) will be reported to the IRB within five calendar days after the PI learns of the event. RNI is any information that might meet the regulatory definition of an unanticipated problem involving risks to subjects or others or serious or continuing noncompliance that might impact the criteria for IRB approval. The report will be submitted to the IRB by the principal investigator or study coordinator. A summary of all UP's and adverse events, including those that do not meet the requirement for RNI, will be submitted with the continuing review. The FDA will be notified of any unanticipated adverse event related to the use of the study device. Notification will be made within 10 days after the Principal Investigator becomes aware of the event.

Confidentiality Procedures:

To protect confidentiality, standard institutional practices will be followed as described in the OHSU Information Security and Research Data Resource Guide (http://ozone.ohsu.edu/cc/sec/isg/res_sec.pdf) to maintain the confidentiality and security of data collected in this study. Study staff will be trained with regard to these procedures.

[figure not shown]
See IRB protocol 19858 for a complete description of the confidentiality and security of the study data collected during this study to be stored in the OregonAPC repository. Paper files will be stored in locked filing cabinets in restricted access offices at OHSU. After the study, source documents will be maintained at the participating clinical center (or offsite record storage facilities) 2 years after a marketing application is approved for our group's decision support device or discontinuance of pursuit of marketing approval.

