the research center at approximately 7am for the inpatient visit. The Dexcom G5 sensor and PDT glucose sensing cannulas will be placed after arrival (see Appendix for a complete description of the PDT device). An 18-22 gauge IV catheter will be placed for blood sampling every 15 minutes after sensor warm-up is complete for measuring blood glucose concentration. After a 2 hour warm-up period for the G5 sensor, glucose will be controlled using the FMPD single hormone mode. The single hormone mode of the controller determines insulin delivery rates based on proportional and derivative error through one t:slim insulin pump. The second t:slim insulin pump will deliver normal saline at the same delivery rates as the insulin. Subjects will eat breakfast and lunch at approximately 11 am and 3 pm respectively. Subjects will have the ability to complete light exercise on a treadmill. The closed loop system will be stopped at approximately 6pm with removal of all devices. See **Figure 1** for a diagram of the study flow.

During the study, the subject will wear one subcutaneous Dexcom™ G5 continuous glucose monitoring (CGM) system. The CGM system will provide sensed glucose data every 5 minutes. The accuracy of the sensed data will be obtained by reference measurements of two YSI venous blood glucose values to calibrate the sensor at the beginning of the closed loop study. Sensed glucose data will be wirelessly transmitted via Bluetooth Low Energy (BTLE) from the Dexcom G5 transmitter to the Nexus 5 master controller every five minutes. The controller is a Google Nexus 5 phone. The smart phone will wirelessly communicate via BTLE to two Tandem t:slim insulin pumps, one for automated insulin delivery and one of automated saline delivery.

A physician or nurse practitioner will be present for study start-up, will be on campus for exercise and will be immediately available on call at all other times. A research nurse will be available at all times. The study investigators retain the authority to modify any aspects of the protocol at his/her discretion if he/she believes the subject's safety is a concern. A study coordinator will be able to access the cloud for monitoring purposes. For safety purposes, all system alerts that are not serviced by the subject will be pushed to the study coordinator/study investigator according to Appendix M.

Figure 1: Study Flow Design

Subject Criteria***Inclusion Criteria:***

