The visit will be conducted in the OCTRI inpatient research unit. A code cart is on site at all locations and a code team is available by page at all times. After arrival at the clinic, women of childbearing potential will receive a urine pregnancy test if the last pregnancy test was more than 7 days prior. This test must be negative before further participation is allowed.

The subject will be asked to check his/her CBG before driving to the clinic and to bring a snack in the car in case hypoglycemia does occur (in which case, the subject must park and treat the hypoglycemia). The subject will arrive at the research center at approximately 7am.

When they arrive, a capillary blood glucose (CBG) will be obtained and measured by a Contour Next glucose meter. Subjects will be given 15-20 grams of oral carbohydrate if the CBG reading is less than 70 mg/dl. CBG values > 300 mg/dl will be managed at the discretion of the investigator with a correction bolus. If carbohydrates or a correction insulin dose is given, blood glucose will be monitored according to the study investigator's orders until the glucose is acceptable to the investigator, and is within the range of 70-300 mg/dl. Serum ketones will also be checked. If the blood ketone value is 0.6 mM or less, the procedure will be started. If serum ketones are ≥ 0.6 mM, the study will be halted and insulin therapy will be guided by the onsite investigator. Ketones will be measured with the Precision Xtra ketone meter. The Precision Xtra meter will undergo quality control testing every 30 days with two different ketone levels, one high and low and both values must fall within the accepted range for a meter to be used.

Subjects will have a Dexcom G5 sensor inserted. The wire glucose sensor is sterile and commercially available from DexcomTM and will be used for single use only as directed by the manufacturer. The sensor will be inserted into the subcutaneous tissue of the abdomen or flank after appropriate preparation of the abdominal skin as per the manufacturer's directions. Subjects will be instructed to discontinue the use of acetaminophen for all periods when wearing the Dexcom CGM system.

[figure not shown]

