At approximately 6pm, the closed-loop study will be terminated and the subject’s own insulin pump will be restarted. The IV catheter will be removed. The study investigator will consult with the subject regarding appropriate insulin dosing for the remainder of the day. The HR monitor and Dexcom G5 sensor will be removed. The glucose sensing cannula units will be slowly removed and the sensor data uploaded. Only trained personnel will be allowed to remove the devices. The personnel who will be allowed to remove the devices will include the investigators (PI, Co-I) and the clinical coordinator. The infusion sites and sensor site will be inspected for signs of erythema/edema and assessed using the Draize Scale (see Appendix F). In addition, the Dexcom G5 sensor and glucose sensing cannulas will be inspected for the possibility of breakage or fracture. If there is any evidence of sensor breakage, it will be recorded. A de-identified photograph will be taken of the sensor insertion areas and the devices. If an area of inflammation of 1 cm or greater exists around the point of insertion, the subject will return 1-3 days later for a follow-up visit.

Due to the fact that the subject’s usual diabetes routine has been interrupted, it is recognized that this final period of time represents an important period for subject safety. As the subject departs from the study center, it will be important for the subject to monitor blood glucose frequently and to be able to call the study physician if questions arise. More specifically, in order to be discharged, subject’s blood glucose must be greater than 90 and less than 300 and the subject

must be feeling well without nausea or other symptoms. If glucose is less than 90, he will be given 15 grams of rapidly acting oral carbohydrate. CBG will be repeated every 15 minutes (with repeat oral carbohydrate treatment if CBG < 90) until CBG exceeds 90, at which time the subject will be discharged.

If blood glucose exceeds 300, the study physician will determine a correction dose of insulin after evaluating the current insulin-on-board value. In addition, blood ketones will be measured. If the ketone value is over 3 mM, the subject will be sent to the OHSU Emergency Department. If the ketone value is between 0.6 and 3.0, the study physician will administer a correction dose, provide oral hydration, and keep measuring blood ketones hourly. The subject will be discharged only when the ketone value is less than 0.6 mM.

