A research staff member will telephone the subject the next day to check on health status.

If a study visit is stopped prematurely, such as due to technical problems, the subject will be asked if they can repeat the study visit that was terminated early with additional compensation provided. Repeating the study visit will be optional.

Hypoglycemia Treatment Guidelines

- **BG < 70 mg/dl**
 - Give 15 grams of oral carbohydrate.
 - Repeat treatment every 15 minutes as needed to raise blood glucose ≥ 70 mg/dl.
- **BG < 50 mg/dl**
 - Verify that insulin pump is turned off
 - Give 100 mL of 10% dextrose through the IV cannula
 - Repeat BG measurement after dextrose infusion complete and repeat process until BG > 70 mg/dl.
 - If no IV access available, give 30 grams of oral carbohydrate, further treatment as per study investigator.
- **Presence of STUPOR, LOSS OF CONSCIOUSNESS, or SEIZURE**
 - Give 1 mg glucagon SC or if IV cannula is patent, 100-300 mL of 10% dextrose STAT. Glucagon will be administered by needle and syringe that are provided with GlucaGen emergency kits.
 - Verify that insulin is turned off.
 - Further management per study investigator.

Hyperglycemia Treatment Guidelines

If the sensed glucose is ≥ 300 mg/dl for longer than 30 minutes or reaches >400 mg/dL, the subject will be instructed to check their blood glucose and study staff will examine the insulin infusion site and will check the subject's serum ketones every hour while sensed glucose is ≥ 300 mg/dl. If serum ketones are over 0.6 mM, the on call study investigator will be alerted to discuss proper management, including changing insulin infusion set and delivering a correction bolus. In addition, the subject will be encouraged to drink sugar-free liquids. If serum ketones are above 1.5 mM at any time, the study will be stopped and insulin will be administered as directed by the on call investigator.

Cleaning and Disinfecting

All devices will be cleaned and disinfected between subjects. The smart phone, Dexcom G5 transmitter, the glucose sensing cannula insertion devices and telemetry units are cleaned by study staff. Technicians who are disinfecting units will wash hands thoroughly and wear gloves. All items will undergo intermediate-level disinfection using SANI-CLOTH AF3 Germicidal disposable wipes. The disinfectant will be applied and allowed to air dry. After disinfection, when the units are completely dry, they will be placed in a sealed bag labeled with subject information.

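### The arrival ketone check both starts and halts the visit at a reading of exactly 0.6 mM

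*Combined protocol and SAP*

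**What the plan says.** The rule is in the protocol section headed 12 hour Treatment Visit, among the checks made on arrival and before any device is inserted. The start condition is "If the blood ketone value is 0.6 mM or less, the procedure will be started". The next sentence gives the halt condition: "If serum ketones are ≥ 0.6 mM, the study will be halted and insulin therapy will be guided by the onsite investigator". The sentence after that names the instrument: "Ketones will be measured with the Precision Xtra ketone meter".

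Two other places use a 0.6 mM limit, each for a different situation:

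- **Discharge**, later in the same section, for a subject whose glucose is above 300 mg/dl at the end of the visit: "The subject will be discharged only when the ketone value is less than 0.6 mM".
- **During the stay**, under Hyperglycemia Treatment Guidelines: "If serum ketones are over 0.6 mM, the on call study investigator will be alerted to discuss proper management".

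Under the same guidelines there is a higher limit: "If serum ketones are above 1.5 mM at any time, the study will be stopped". On staffing, the Protocol Summary says "A physician or nurse practitioner will be present for study start-up".

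**The concern.** A go/no-go rule should give one instruction for every possible reading, above all at its own threshold. Here both limits are inclusive, so they overlap at the cut-off and call for opposite actions.

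This is the only ketone reading that decides whether the visit goes ahead. What follows a start is the insertion of two investigational cannulas, removal of the subject's own infusion set, and automated insulin delivery through one of the investigational cannulas. Staff who see 0.6 mM cannot comply with both sentences. Two subjects with the same reading could be handled differently, each with support in the text.

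**Working it through.** The plan has no figure to reproduce here; the check is a comparison of two sets of readings.

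**Inputs**, all from the arrival checks. Let k be the ketone reading in mM.

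- Start rule: S = {k ≤ 0.6}.
- Halt rule: H = {k ≥ 0.6}.
- Measurement: one check, one named meter. One sentence speaks of blood ketones and the other of serum ketones, but the protocol describes no second assay, so both refer to the same k.

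**Overlap.** S ∩ H = {k ≤ 0.6} ∩ {k ≥ 0.6} = {0.6}. Exactly one value receives two instructions, and they are incompatible.

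| Reading (mM) | Current rules | Start if k < 0.6, halt if k ≥ 0.6 | Start if k ≤ 0.6, halt if k > 0.6 |
|---|---|---|---|
| 0.5 | start | start | start |
| 0.6 | **start and halt** | halt | start |
| 0.7 | halt | halt | halt |

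Making either limit strict empties the overlap, and only the outcome at 0.6 mM changes.

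**Does any other text settle it?**

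- The discharge rule treats 0.6 mM as not yet acceptable.
- The in-study alert acts only above 0.6 mM, so 0.6 mM does not trigger it. The two neighbouring rules therefore fall on opposite sides of the cut-off, and neither is a rule for starting.
- Stopping Rules uses ketones only at more than 1.5 mM, together with glucose above 250 mg/dl.
- The conflict clause under Monitoring Procedures concerns competing laws and guidelines, not two sentences of the protocol.

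None of these says which arrival sentence governs.

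**Exposure.** With one reading per visit there are 10 subjects × 1 visit = 10 readings, plus any optional repeat visits. The arrival text can also be read as asking for ketones only when carbohydrate or a correction dose was given, in which case there would be fewer. The documents give neither the meter's resolution nor how often 0.6 mM would be read, so no probability can be attached.

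**The case against.** The case on the other side is about weight, since the overlap itself cannot be denied.

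- **Little follows from either choice.** A subject started at 0.6 mM has blood glucose measured every 15 minutes, hourly ketone checks in sustained hyperglycemia, and a stop above 1.5 mM. A subject who is halted receives insulin under the investigator's guidance. This stands, and it keeps the point small.
- **Investigators may modify the protocol when they believe safety is at risk** (Protocol Summary). This gives a documented route to halting at 0.6 mM, so halting on that ground need not count as a deviation. It permits a judgement, but it does not state a rule or make handling consistent between subjects.
- **The documents do not dictate the repair.** The discharge rule favours a strict start limit, while the in-study alert favours starting at 0.6 mM. This also stands: both repairs are coherent, and the choice between them is a preference for caution. The discharge rule is the closer analogue, because it too decides whether a subject may proceed. The alert only prompts a call about a subject already in the study.

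**Conclusion.** The concern holds. For one arrival reading, exactly 0.6 mM, the protocol gives opposite instructions, and no other text resolves them. Every other reading gets a single instruction.

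The conclusion rests on both sentences referring to the same meter reading, which the text supports. The practical effect is small, and neither the endpoints nor the analysis are touched. The point is a drafting inconsistency in an operative safety rule; it should be corrected, but it does not threaten the study.

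**What to change.** In the start sentence, replace the inclusive limit with *less than 0.6 mM*, and keep the halt limit at 0.6 mM or above. The discharge rule and the hyperglycemia guidelines need no change. If the investigators prefer to start at 0.6 mM, the alternative is to halt only above 0.6 mM; either version removes the conflict, but the first is the cautious one.

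The cost is one inequality in one sentence and no added procedure, presumably with a minor amendment, since the protocol is IRB-approved. A subject at exactly 0.6 mM would be halted. The text does not say whether that means a pause and recheck or the end of the visit, so in the worst case the visit is lost for that day.
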